5. MONITORING AND AUDIT

Study Monitoring

The study will be monitored by the Principal Investigator at periodic intervals during the course of the study to ensure that the study is being conducted according to Good Clinical Practice.

The Investigators will be contacted by the PI on a regular basis. On this occasion, the progress of the study will be discussed with the Investigator and the CRFs will be checked for completeness and consistency and to verify compliance with the study protocol.

6. SUBJECT TERMINATION/WITHDRAWAL PROCEDURES

All efforts will be made to determine the reason(s) why a patient is withdrawn from the study. Subjects could be withdrawn from the study if any of the following occur:

1. Subject fails to substantially comply with the protocol requirements;
2. Subject develops a serious adverse reaction. The Study Investigator will immediately notify the PI and information will be recorded on a Serious Adverse Event Form (Appendix 3);
3. Subject elects to terminate participation in the study. Participation in the study is voluntary. A subject has the right to withdraw from the study at any time for any reason.

The Investigator may terminate the study at any time if the risk-benefit ratio is no longer favourable. Before discontinuation, the Investigator should inform the PI and ask for advice. If the Investigator is concerned about continuation of the study, his/her concerns should be transmitted immediately to the PI.

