The **principal investigator's** responsibilities are described in detail in ISO norm 14155:2011 for the clinical investigation of medical devices for human subjects.

The role of the principal investigator is to implement and manage the day-to-day conduct of the clinical investigation as well as ensure data integrity and the rights, safety and well-being of the subjects involved in the clinical investigation.

The principal investigator shall be qualified by education, training and experience to assume responsibilities for the proper conduct of the clinical investigation. In particular, the principal investigator is responsible for:

- qualification of investigation site;
- communication with Ethics Committee;
- compliance with Informed Consent process;
- compliance with Clinical Investigation Plan.

Under the direct supervision of the Principal Investigator, certain duties may be delegated during the course of the study. These responsibilities will be documented on the transfer of responsibilities form maintained in the Investigator Site file.

The **Statistician** will be responsible for:

- sample size calculation;
- statistical plan;
- statistical section of the protocol;
- statistical evaluation;
- final statistical report.

OBJECTIVE

The study will be performed to assess the efficacy of disclosing plaque agent (DPA) and erythritol powder to remove biofilm and plaque in pediatric patient during professional oral hygiene.

INTRODUCTION

In the mouth of the patients the biofilm is not always evident, so its removal can be difficult. Using the disclosing plaque agent before the therapy as a guide to remove the biofilm may be a solution. Thanks to this tool, we can clearly see where the plaque is, so its removal can be easier. In pediatric patients is more difficult to remove biofilm and plaque cause of less collaboration to a correct oral hygiene. Probably, using a disclosing plaque agent that guide the operator, could give more security and faster for a better removal of the biofilm. Moreover, the use of low abrasiveness powder could lead to several advantages like a decrease of patients' uncomfortable feeling, the shortest execution time and the possibility of cleaning areas with difficult access and the less damage on soft and hard tissue respect the traditional professional oral hygiene.

For this reasons, we decided to study the efficacy of this method.

STUDY OUTCOMES

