Primary outcome measure: comparison between groups of the percentage of area in which the disclosing plaque agent is present (RPA: Residual Plaque Area).

RPA: residual plaque area: percentage of area with residual plaque coloured by disclosing plaque agent. This will be calculated with a ImageJ Software.

Secondary outcome measure:

- comparison between groups of FMPS (Full Mouth Plaque Score) after professional oral hygiene – clinical parameter
- comparison between groups on execution time
- comparison between groups about feeling of patient ad operator

STUDY POPULATION

One hundred and twenty (120) children, aged 6-12 years, will be entered into study (randomized). It is expected that forty (120) subjects will complete the study.

Randomized subjects who deviate from the protocol (major protocol deviation) and, for this reason, are excluded from the analysis, will be replaced to guarantee that the sample required for the analysis (120) is reached.

Patient will be treated at the Department of Surgical Specialities Radiological Science and Public Health, School of Dentistry, Section of Periodontics, Brescia, Italy from 01/2023.

Inclusion Characteristics

- Signed Informed Consent Form (pediatric patient and parent).
- Male and female subjects, aged 6 -12 years, inclusive.
- Good general health (ASA I e II)
- With at least 80% of dental formula
- With at least 8/12 frontal dental elements.

Exclusion Characteristics

- Not willing to follow the agreed protocol.
- Presence of orthodontic appliances.
- Tumors or significant pathology of the soft or hard tissues of the oral cavity.
- Current radiotherapy or chemotherapy.
- History of allergy to Erythritol.
- History of adverse reactions to lactose or fermented milk products.

A written informed consent will be obtained from each included patient after explanation of the risks and benefits of participating to this study. No change in the trial design will be made after approval of the Ethical Committee.

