1. STUDY DESIGN

The study design was chosen according to the current standards required by GCP and according to national requirements.

- a. A 2 by 2 parallel design.
- b. The RCT will be run as mono-center;
- c. A total of 120 subjects will be recruited to participate in the study. It is expected that all of 120 subjects will complete the study in total;
- d. Admission into the study will be via rolling admission (estimated recruitment time: 36 months);
- e. Each subject must be pediatric patient who needs a professional oral hygiene;
- a. Each subject will follow the following treatment protocol:
 - i. - Visit (T0): consent secured; screening and entry into study; baseline data collection (FMPS), randomization into one of the four treatment arms as per the randomization protocol;

ii. - Treatment (T0): all patients will receive a full-mouth professional oral hygiene. Procedures will be performed in the following chronological sequence:

- A. Place Optragate
- B. Start the timer for the executive time
- C. According to the randomization list, patients assigned to the **GBT+** will do professional oral hygiene guided by disclosing plaque (GBT):

- Placement the disclosing plaque agent (Biofilm Discloser® (EMS Electrical Medical Systems SA, CH 1260-Nyon, Switzerland)) on the teeth and rinse with only water;
- Tissue decontamination with Air-flow (Air-flow® Prophylaxis Master EMS, Nyon Switzerland) and erythritol powder (PLUS powder® EMS, Nyon Switzerland);
- Supragingival removal biofilm with Air-flow (Air-flow® Prophylaxis Master EMS, Nyon Switzerland) and erythritol powder (PLUS powder® EMS, Nyon Switzerland);
- Subgingival removal biofilm with Air-flow (Air-flow® Prophylaxis Master EMS, Nyon Switzerland) and erythritol powder (PLUS powder® EMS, Nyon Switzerland);
- Calculus removal with piezoceramic device (Air-flow® Prophylaxis Master EMS, Nyon Switzerland), with a slim tip (PS® EMS, Nyon Switzerland);
- The treatment ends, when all the disclosing plaque has been removed;
- Stop the timer and note the executive time;
- Questionnaire patient and operator;
- Placement of the disclosing plaque agent (Biofilm Discloser® (EMS Electrical Medical Systems SA, CH 1260-Nyon, Switzerland)) on the teeth and rinse with only water;
- Note the FMPS;
- Collection of the pictures.

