11. ETHICAL ASPECTS AND REGULATIONS

Ethical Conduct of the Study

This study is to be conducted in accordance with the ethical principles of the Declaration of Helsinki and according to local laws and regulations.

Independent Ethics Committee (IEC) and Relevant Authorities

Before starting the study, the study protocol will be subject to review by the Ethical Committee of the University-Hospital of Brescia. As required by law, the study will be notified to authorities if applicable. No subject should be admitted to the study before the Ethical Committees issue their written favourable opinion of the study. Periodic status reports must be reported to the ethics committee at least annually as well as notification of the completion of the study. The investigator

must maintain an accurate and complete record of all reports and documents submitted to and received from the ethics committee according to the ISO 14155:2011 Clinical Investigation of Medical devices for human subjects.

Subject information and Informed consent form

The purpose and description of the study in lay language, possible adverse reactions, risks and benefits of participation and the subject's right to withdraw without prejudice at any time must be explained to each subject. Each subject must read, understand and sign the informed consent form provided before any study-related procedure.

Subject data protection and Confidentiality

The name of the subject as well as all other personal data will be kept strictly confidential by the Investigator. If due to medical reasons, it is necessary to identify the subject during the study course, this will be done under medical secrecy.

The subject has given his/her consent before the beginning of the study. In case of withdrawal of this consent subject has to leave the study.

All subjects will agree to verify, by letter, that they participated in this study, if called upon to do so.

New Findings

Subjects will be informed of any significant new findings related to study products or procedures when they become known during the course of this clinical research study. Such information may affect the subject's decision to continue participation in the study.

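### The plan does not separate stopping the cleaning from leaving the study, so residual plaque may go unrecorded, or be excluded and replaced, in children whose cleaning was not finished

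*Combined protocol and SAP*

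**What the plan says.** Section 6 opens with "Subjects could be withdrawn from the study if any of the following occur" and lists three grounds: "Subject fails to substantially comply with the protocol requirements", a serious adverse reaction, and the subject's own choice. It does not mention a cleaning that is stopped while the child remains in the study. Section 11 adds, for consent, "In case of withdrawal of this consent subject has to leave the study".

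Section 1, item C (GBT+), gives the order of steps: "The treatment ends, when all the disclosing plaque has been removed", then "Stop the timer and note the executive time", then the questionnaires, a fresh application of dye, FMPS and "Collection of the pictures". Item E (US+C+) repeats this order. Items D and F refer back to it for the two arms without initial dye. No branch covers a session that ends in another way. Section 3 places the whole treatment in one session.

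Study Population says that randomised subjects with a major protocol deviation who for that reason "are excluded from the analysis, will be replaced to guarantee that the sample required for the analysis (120) is reached". The term is not defined. Section 4 defines a safety set, but no efficacy set and no rule for missing RPA. Section 1 expects all 120 children to complete. Section 2 lists only the statistician as blinded, and Section 1, item G, has one clinician give every treatment.

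**The concern.** A child aged 6 to 12 may not sit through a full-mouth session. The Introduction gives "less collaboration to a correct oral hygiene" as a reason why plaque is harder to remove in children, and hopes that the powder will be less uncomfortable. It is therefore plausible that stopping is related both to residual plaque and to technique.

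If RPA is not taken in such a child, or is taken and then excluded, the analysed children are selected after randomisation on something related to the outcome. Filling the place with a new child brings the number back to 120 but leaves the selection in place. With no later visit, an RPA that was not recorded cannot be recovered. A timer read at an early stop would also count as a fast treatment in the execution-time comparison.

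**Working it through.** **Inputs from Section 4:** mean RPA 10% in both arms without initial dye, 2.9% in US+C+, 1.5% in GBT+; phi = 55; 30 per arm; 5% significance; stated power 83% for the interaction. The link function and the sidedness are not stated. I assume a logit link and a two-sided test.

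**Planned interaction.** I = [logit(GBT+) − logit(US+C+)] − [logit(GBT−) − logit(US+C−)] = (−4.185 + 3.511) − 0 = −0.674.

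**The plan's own power.** The standard error from the Fisher information with 30 per arm is 0.227, so power = Φ(0.674/0.227 − 1.96) = 84.3%. Simulation with values bounded at 0.0001 gives 84.4%. The stated 83% is reproduced closely enough to support the assumed link and two-sided test. With 27 per arm (10% lost, not replaced) the standard error is 0.239 and power 80.4%. Lost numbers are therefore a minor issue; selection is the main one.

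**Effect of leaving out unfinished cleanings.** The documents give neither a stopping rate nor an RPA for such children. I assume a share s of 5% or 10%, with RPA r of 10% to 20%, and that completers have the planned means. The mean over all children in an arm is (1 − s) × planned mean + s × r.

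- s = 5%, r = 10%, every arm: US+C+ = 0.95 × 2.9 + 0.05 × 10 = 3.255%; GBT+ = 0.95 × 1.5 + 0.05 × 10 = 1.925%; the other two stay at 10%. I = −3.931 + 3.392 = −0.539, a shift of 0.135.
- s = 10%, r = 20%, every arm: US+C+ = 0.9 × 2.9 + 0.1 × 20 = 4.61%; GBT+ = 0.9 × 1.5 + 0.1 × 20 = 3.35%; the other two are both 11%. I = −3.362 + 3.030 = −0.332, a shift of 0.34.

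The same formula with stopping that differs by technique:

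| Share stopping, US arms / GBT arms | I over all children, r = 10% to 20% | Completers only (−0.674) |
|---|---|---|
| 5% / 5% | −0.539 to −0.451 | overstates |
| 10% / 10% | −0.442 to −0.332 | overstates |
| 10% / 5% | −0.646 to −0.613 | slightly overstates |
| 10% / 0% | −0.900 to −1.048 | understates |

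Much of the shift under equal stopping comes from the logit scale. In percentage points the planned US+C+ minus GBT+ difference of 1.4 becomes 0.95 × 1.4 = 1.33 or 0.90 × 1.4 = 1.26.

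**Check by fitting the model.** Simulated trials (1000 runs each; 5% to 10% unfinished, assumed RPA 15% or 25% in those children) were analysed by beta regression. Completers only, not replaced: interaction about −0.66, power 80% to 82%. With all 120 measured:

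- 5% unfinished in every arm: −0.61 or −0.56, power 74% or 61%.
- 10% unfinished in every arm: −0.56 or −0.50, power 62% or 44%.
- 10% in US and 5% in GBT: −0.64 or −0.58, power 75% or 61%.

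The fitted values are not the logits of the arm means, because the model imposes one precision on a mixed population. In these scenarios the direction agrees with the arithmetic above.

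**The case against.** The strongest reply is that this turns silence into a rule. Section 6 is permissive, and inability to finish is not named as a ground. Section 4 recognises treatment being stopped or reduced, although only as a category for tabulating adverse events. Section 1 lists an order of steps and nowhere makes the final dye and pictures conditional on complete plaque removal. Its end rule cannot even operate as worded in the two arms without initial dye. Sections 6 and 10 already ask for withdrawal reasons and for deviations and withdrawals to be reported. Section 7 provides a blind data review.

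Much of this stands. A reader might infer that withdrawal is the only exit and that RPA is then lost. The documents do not say so; loss is a possible consequence. A reader might infer that these children have the most plaque, or cannot tolerate the session. The Introduction says only that lower cooperation makes plaque harder to remove. A reader might also place all stopping in US+C+ and set the resulting logit shift of 0.12 to 0.48 (mean 3.26% to 4.61%) against the planned 0.67. That misleads: equal stopping moves the interaction by a similar amount, and in the opposite direction.

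What does not stand is the idea that discretion is a safeguard. Study Population does state exclusion and replacement, with no definition of the deviation. The treating clinician knows the arm. The data review is not described as deciding exclusions, and it cannot supply an RPA that was never recorded. Reporting reasons does not restore the comparison.

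**Conclusion.** The point holds as a gap in outcome collection and in the analysis population. Read together, Study Population and Sections 1 and 6 allow children with an unfinished cleaning to be unmeasured, or excluded and replaced, in a way that may be related to the outcome and to the arm.

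How often this would happen is unknown, and so is the direction of the bias. The shift of about 0.13 to 0.34 against 0.67 rests on assumed equal stopping of 5% to 10%, assumed RPA of 10% to 20% in those children, and a logit link. With 10% stopping in the US arms and none in the GBT arms, the interaction over all children is larger than in completers. A claim that the plan favours one technique is therefore not supported. Children who withdraw consent, or who refuse the dye and pictures, would be missing under any wording.

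**What to change.** - In Study Population, Section 1 (items C to F) and Section 6, separate an unfinished cleaning from withdrawal from the study. State that every randomised child who still consents, and for whom the investigator sees no clinical reason against it, has the already planned final dye, FMPS, pictures and questionnaire at T0, whatever part of the cleaning was completed.
- Analyse these children in their randomised group. Remove their exclusion and replacement from the primary analysis, and define major protocol deviation.
- Add a CRF field for cleaning completed (yes/no, reason) and report it by arm.
- Treat the timer reading of an unfinished session as censored, not as a short execution time.

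When cleaning or any study procedure is stopped remains a clinical decision and is not changed.

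The cost is protocol wording and one CRF field, with no new procedure. Section 9 gives the amendment route; the statement in Study Population that the design will not change after approval has to be reconciled with it. The downsides are a few extra minutes with a tired child, some values still missing through refusal, and possibly a smaller observed interaction with less power than the stated 83%.

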7. DOCUMENTATION AND DATA MANAGEMENT

Data collection in the case report form (CRF)

All study data will be recorded in the case report forms identified by the subject number. Only the principal investigator, co-investigators, or designated study personnel may make entries in the case report forms.

The Investigator has to identify all data that were directly recorded into the CRF and to be considered to be source data.

The CRFs will be checked for completeness and plausibility by the PI. The Investigator will resolve any queries.

Investigator Site File (ISF)

The ISF includes all documents that are required for the clinical study. During monitoring, the ISF will be checked regularly for completeness and actuality. After the clinical trial is finished or stopped, the ISF has to be stored 15 years in the study center.

Data Management

Data extraction from CRFs into a single, electronic database is performed by examiners. Discrepancies are to be clarified and corrected by authorized persons by means of documented data queries between Statistician and Investigator(s).

After the study is finished and before data are analyzed, a blind data review meeting will be held between the investigator and the statistician. When the database has been declared to be complete and accurate, it will be locked. Any changes to the database after this procedure can only be made by joint written agreement among the clinical trial leader, the trial statistician, and the co-investigators.

8. ADVERSE EXPERIENCES/EVENTS

Subjects will be informed of any possible adverse reactions which they could experience and will be instructed to immediately report any event to the investigator. The investigators will record any and all adverse reactions and report this documentation to the Principal Investigator. In the event of an adverse experience, emergency or other problems or questions regarding participation in this study, the subject can contact the following investigators:

for Brescia Site: (Principal Investigator)

Adverse Events (AEs) and Serious Adverse Events (SAEs) are defined by the ICH Guideline Medical Device Directive 93/43/EEC and Guidelines on Medical Devices MEDDEVG 2.7/3rev. 3, May 2015 Clinical Investigations: Serious Adverse Event Reporting under Directives 90/385/EEC and 93/42/EEC for Good Clinical Practice (ICH GCP) as follows:

An adverse event (AE) is any untoward medical occurrence, unintended disease or injury or any untoward clinical signs (including an abnormal laboratory finding) in subjects, users or other persons whether or not related to the investigational medical device.

With respect to intensity, adverse events are classified as follows:

- Mild Some awareness of symptoms, but easily tolerated;
- Moderate Symptoms causing enough discomfort to interfere with usual activity;
- Severe Incapacitating event causing inability to work or to perform usual activity.

Adverse events are classified as either non-serious or serious.

Serious Adverse Event (SAE) is an adverse event that:

- a) led to a death;
- b) led to a serious deterioration in health of the subject, that either resulted in:
 - a life-threatening illness or injury, or
 - a permanent impairment of a body structure or a body function, or
 - in-patient hospitalization or prolongation of existing hospitalization, or
 - in medical or surgical intervention to prevent life threatening illness or
 - injury or permanent impairment to a body structure or a body function.
- c) led to fetal distress, fetal death or a congenital abnormality or birth defect.

Device deficiency: inadequacy of an investigational medical device related to its identity, quality, durability, reliability, safety or performance. This may include malfunctions, use error, or inadequacy in the information supplied by the manufacturer.

AEs include any clinically significant deterioration of a subject's medical status, after being enrolled and signing an informed consent form. The AE may involve any organs or systems and can be represented by the new onset or the deterioration of a disease, a syndrome, a symptom, a physical

sign, as well as by findings and results of instrumental examinations and laboratory tests. Any medically relevant and untoward change from baseline, including frequency or pattern changes for a fluctuating condition (e.g., migraine), occurring after the administration of investigated treatments is an adverse event. All such occurrences must be recorded and reported accordingly, whether they appear causally related to the study medication, or not.

Serious Adverse Device Effect (SADE) is an adverse device effect that has resulted in any of the consequences characteristic of a serious adverse event.

Unanticipated Serious Adverse Device Effect (USADE) is a serious adverse device effect which by its nature, incidence, severity or outcome has not been identified in the current version of the risk analysis report or investigator's brochure (IB).

NOTE: Anticipated SADE (ASADE): an effect which by its nature, incidence, severity or outcome has been previously identified in the risk analysis report or IB.

The following events are considered reportable:

- any SAE;
- any Device Deficiency that might have led to a SAE if:
 - a) suitable action had not been taken or
 - b) intervention had not been made or
 - c) if circumstances had been less fortunate;
- new findings/updates in relation to already reported events.

Reportable events have to be reported by clinical investigators.

Assessment of Causality

The following criteria are to be used for the assessment of the causal relationship to the test/control treatment. For classification, all criteria of one of the following categories must be met:

related, if

- a timely correlation exists and
- dechallenge and/or rechallenge and
- a biological plausibility exists and
- other factors are clearly excluded

- a medical report or clinical proof exists;

possibly related, if

- a timely correlation exists and
- dechallenge and/or rechallenge and
- a biological plausibility exists and
- a medical report or clinical proof does not exist;

unrelated, if

- a timely correlation does not exist or is uncertain and
- dechallenge and/or rechallenge does not exist and
- a biological plausibility exists and
- a medical report or a clinical proof does not exist;

unknown, if

- not enough information exists for evaluation
- no further contact with reporter possible.

Sound medical/clinical judgment will be applied when assessing the causality and seriousness of the adverse events.

Adverse Event Reporting

The study center will provide the study participants with emergency telephone numbers for study related support and feedback. The emergency telephone number is operated by either an investigator of the study or by a qualified person designated by the principal investigator. The schedule of reachability of the emergency telephone number will be defined prior to start of the study.

Serious Adverse Events

The Investigator shall immediately after awareness (and in any event, not later than within 24 hours after awareness) inform the PI. The Investigator will send the SAE report to the following email address. Appendix 3 has to be used for SAE reporting. Form has to be completed electronically and in English.

Adverse Events

Adverse events will be assessed by the investigator or designee within 24 hours for severity, relationship to the study product, possible etiologies, and whether the event meets the criteria as a serious adverse event and therefore requires immediate notification to the PI. For data collection purposes, the outcome of all adverse events recorded on the Adverse Reaction section of the CRF will be designated as of the completion of the final evaluation or examination. However, the investigator is responsible for following all adverse events until resolution or until no longer of clinical concern, and providing these data to the PI. At the end of the study, the investigator will report all adverse events (serious and non-serious) to the PI on CRFs. Forms have to be completed electronically and in English.

Pregnancy

No pregnant women (according to medical history) will intentionally be enrolled in this study. In the event a woman enrolled in this clinical research study becomes pregnant during the course of the study, participation in this study will be terminated upon the clinical staff's notification of the event. The subject's medical records used in this study will be updated to reflect the pregnancy and there will be follow- up contact until the end of the pregnancy to record the outcome in the clinical file.

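### The adverse-event causality list requires biological plausibility even for 'unrelated', so an assessable implausible event has no category; read literally, some timely, plausible events can also drop out of one safety count

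*Combined protocol and SAP*

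**What the plan says.** All references are to the combined protocol and SAP. Section 8, Assessment of Causality, gives the rule: "For classification, all criteria of one of the following categories must be met". The categories are:

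- *Related*: timely correlation; dechallenge and/or rechallenge; "a biological plausibility exists and"; "other factors are clearly excluded"; "a medical report or clinical proof exists". No linking word is printed between the last two.
- *Possibly related*: timely correlation; dechallenge and/or rechallenge; the same plausibility line; "a medical report or clinical proof does not exist".
- *Unrelated*: "a timely correlation does not exist or is uncertain and"; "dechallenge and/or rechallenge does not exist and"; again "a biological plausibility exists and"; "a medical report or a clinical proof does not exist".
- *Unknown*: too little information to evaluate, or the reporter can no longer be reached.

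A closing sentence asks for sound clinical judgment on causality and seriousness. Section 3 (Treatment) says that the whole mouth is treated in one session. Section 4 (Evaluation of Safety) plans, per treatment group, the number of AEs, the number at least possibly related to treatment, and the number of patients with at least one AE.

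**The concern.** Plausibility is required in all three substantive categories. For *unrelated* this runs against the sense of the category: an event that the device could not plausibly have caused is barred from it. *Unknown* is no refuge, because it is for missing information, not for a fully assessed event that matches nothing.

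The second issue depends on how the text is read. *Related* and *possibly related* both carry a dechallenge/rechallenge line that has no verb and no definition. After one treatment session it is unclear what would satisfy it. A third, narrower issue is that *possibly related* requires the absence of a medical report or proof. An event that has a report, but whose other possible causes are not excluded, can then miss both categories.

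What is at stake is one planned descriptive output, the per-group count of AEs at least possibly related to treatment. A timely, plausible event left without a category is not in that count.

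**Working it through.** The plan gives no figure to reproduce, so the check is one of logic. Code each criterion yes or no: T timely, D dechallenge/rechallenge, P plausible, O other factors excluded, M medical report or proof. *Unknown* is left out because every pattern here is fully assessed. The counts are logical patterns, not event frequencies.

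**As printed**, 2^5 = 32 patterns:

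- *Related* = T, D, P, O, M all yes: 1 pattern.
- *Possibly related* = T, D, P yes and M no, O free: 2 patterns.
- *Unrelated* = T no, D no, P yes, M no, O free: 2 patterns.

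Classified: 1 + 2 + 2 = 5 of 32, with no overlaps. If uncertain timing is kept separate from absent timing there are 3 × 2^4 = 48 patterns, of which 1 + 2 + 4 = 7 are classified.

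**Implausible events.** With P = no there are 2^4 = 16 patterns (24 with three timing levels). None is classified, because all three categories need P = yes.

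**Timely, plausible events.** With T = P = yes there are 2^3 = 8 patterns, of which 1 + 2 = 3 are classified and 5 are not. Four of the five have D = no. The fifth has D = yes and M = yes, but O = no. None of the five can be *unrelated*, since timing exists.

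**Other readings of the same text:**

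| Reading | Timely, plausible patterns with no category |
|---|---|
| Literal | 5 of 8 |
| 'Or' between the last two *related* lines | 4 of 8, and 1 pattern (D yes, O yes, M no) in two categories |
| Event resolves and this counts as dechallenge | 1 of 4 |
| The same, and proof implies other factors excluded | 0 of 3 |
| Event does not resolve, line still required | 4 of 4 |
| Line read as 'if applicable', and not applicable | 1 of 4 (M yes, O no) |

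With the 'if applicable' reading, the one pattern left also disappears if clinical proof means proof of causation. The result for implausible events is the same on every row, because no row touches that line.

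**Does reversing the plausibility line repair the list?** *Unrelated* would become T, D, P, M all no, O free: 2 patterns. The total stays 1 + 2 + 2 = 5. Two implausible patterns gain a category, and the two plausible patterns now classed *unrelated* lose theirs. *Related* plus *possibly related* stays at 3.

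**Does the proposed amendment work?** Delete the plausibility line from *unrelated*: T, D, M all no, with P and O free, gives 4 patterns. Define *possibly related* as T and P yes but not all of *related*: 8 − 1 = 7 patterns. Classified: 1 + 7 + 4 = 12, with no overlaps. Left over: 32 − 12 = 20. Of these, 8 are timely but implausible. The other 16 − 4 = 12 are not timely but have dechallenge or a report (6 plausible, 6 implausible).

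**The case against.** The strongest reply is that nobody would apply the list so mechanically. Section 8 calls for sound clinical judgment and has each AE assessed within 24 hours for relationship and possible etiologies. Section 7 adds CRF checks, documented data queries and a blind data review meeting before analysis. An AE that silently lacks a category is therefore less likely than the logic alone suggests. This stands as mitigation. But none of these provisions says which category an unmatched event receives, so two assessors could place the same event differently.

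The second reply is that the dechallenge line, having no verb, can fairly be read as applying only where dechallenge is possible. This also stands. It shrinks the gap for timely, plausible events to one pattern, and perhaps to none. The words 'if applicable' are not printed, however, so the literal reading remains open. The reply does nothing for implausible events.

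A reader might infer more than the documents support:

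- *That the plausibility error lowers the related count.* It does not. The events that it strands are implausible ones, which could not have been *related* or *possibly related* anyway.
- *That most adverse events will go unclassified, since 27 of 32 patterns do.* Patterns are not events. Some may be rare, and no AE rate is given.
- *That the safety evaluation as a whole is compromised.* Total AEs, patients with an AE and the organ-system tables do not use causality, and any SAE is reportable whatever its cause.

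**Conclusion.** Wrong as written, but minor. The certain part is that an assessable event without biological plausibility fits no category (0 of 16 patterns), on every reading examined. The conditional part is that, read literally, 5 of 8 timely, plausible patterns fit neither *related* nor *possibly related*. If such events are left uncategorised, the per-group count of AEs at least possibly related can be too low. That conclusion assumes yes/no criteria, enough information to assess the event, and no informal assignment by the investigator. How many events are affected, and whether the shortfall would differ between groups, cannot be estimated from the documents. The RPA analysis is untouched. Because the rule is operative and inexpensive to correct, it should be amended, but the trial does not depend on it.

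**What to change.** Amend the causality list in section 8:

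1. Delete the plausibility line from *unrelated* rather than reversing it, so that no pattern now classified loses its category.
2. Keep the *related* criteria, and define *possibly related* as a timely, plausible event that does not meet all of them. Do not require dechallenge/rechallenge or the absence of a medical report.
3. Print the missing 'and' before the last *related* line if all five criteria are meant. (If the last two are alternatives, the timely, plausible patterns split 3 *related* and 5 *possibly related* instead of 1 and 7; all 8 are still covered.)

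On the five-criterion reading this gives 1 *related*, 7 *possibly related* and 4 *unrelated*, with no overlaps. It does not finish the job. Of the 16 implausible patterns only 2 gain a category, and 20 of 32 patterns overall remain unassigned. The sponsor must reconcile these so that each event falls in exactly one category, and must state how uncertain timing is handled.

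The cost is a short protocol amendment. The count of possibly related AEs may rise, because timely, plausible events that might have gone uncategorised would now be included.
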